9.2.2 Demographics and Baseline Characteristics

Demographics and baseline characteristics will be summarized based on the FAS by cohort and overall.

Demographic data will include the following:

- Age (in years)
- Sex (female and male)
- Ethnicity (Hispanic or Latino, not Hispanic or Latino, and not collected per local regulations)
- Race (White, Black or African American, Asian, American Indian or Alaska Native, Native Hawaiian or other Pacific Islander, Other, Not collected per local regulations, Other, and Multiracial [if more than 2 races reported from a subject])

Baseline and disease characteristics will include the following:

- Weight (kg)
- Height (cm)
- BMI (kg/m²)
- *APOL1* genotype (*G1/G1*, *G2/G2*, or *G1/G2*)
- UPCR (g/g)
- UACR (g/g)
- eGFR (mL/min/1.73 m²)
- eGFR (mL/min/1.73 m²) category (<40, ≥40 to <60, ≥60)
- Systolic blood pressure (mmHg)
- Diastolic blood pressure (mmHg)
- Prior medication of any systemic corticosteroid (Yes, No)
- Prior medication of any immunosuppressants (Yes, No)

- Prior medication of any angiotensin converting enzyme (ACE) inhibitor (Yes, No)
- Prior medication of any angiotensin II receptor blocker (ARB) (Yes, No)
- Prior medication of any neprilysin inhibitor (Yes, No)
- Prior medication of any sodium-glucose cotransporter-2 (SGLT2) inhibitor (Yes, No)
- Prior medication of any diuretic (Yes, No)
- Prior medication of any renin inhibitor (Yes, No)
- Prior medication of any statin (Yes, No)
- Medical history of diabetes (Yes, No)

In addition, data listings will also be provided for:

- Informed consent
- Inclusion/Exclusion criteria violation for subjects with any such violations

9.2.3 Medical History

Medical history will be coded by using the Medical Dictionary for Regulatory Activities (MedDRA). Medical history will be summarized descriptively based on the FAS by MedDRA system organ class (SOC) and preferred term (PT). This summary will be provided by cohort and overall. The corresponding data listing will also be provided.

9.2.4 Prior and Concomitant Medications

Medications will be coded using the World Health Organization Drug Dictionary and categorized as the following for the purpose of analysis:

Prior medication: Medication that started before the first dose of study drug, regardless of when dosing of the medication ended

Concomitant medication: Medication continued or newly received on or after the date of the first dose of study through the end of the TE Period

Post-treatment medication: Medication continued or newly received after the TE Period

A given medication may be classified as a prior medication, a concomitant medication or a post-treatment medication; both a prior and a concomitant; both concomitant and post-treatment; or prior, concomitant, and post-treatment medication.

Note that medication that started before the first dose of study drug and continued after the first dose will be categorized as prior medication and separately as concomitant medication. If a

medication has a missing or partially missing start/end date or time and if it cannot be determined whether it was taken before the first dose of study drug, concomitantly during the TE Period, or after the TE Period, it will be considered in all 3 categories of prior, concomitant medication, and post-treatment medication.

Missing or partial dates will be imputed for medication. Details for imputing missing or partial start and/or stop dates of medication are described in [Appendix B](#).

Prior medications and Concomitant medications will be summarized based on the FAS by Preferred Name. This summary will be provided by cohort and overall. Post-treatment medications will only be listed.

9.2.5 Study Drug Exposure and Compliance

Study drug exposure (in days) will be calculated as (last date of dosing – first date of dosing) + 1, regardless of study drug interruption, and will be summarized descriptively based on the Safety Set by cohort and overall. Study drug exposure (in weeks) will be summarized in categories for Treatment Period: ≤ 1 week, >1 to ≤ 2 weeks, >2 to ≤ 3 weeks, >3 to ≤ 5 weeks, >5 to ≤ 9 weeks, >9 to ≤ 12 weeks, and >12 weeks using counts and percentages.

Study drug compliance will be calculated as $100 \times [1 - (\text{total number of days of study drug interruption}) / (\text{duration of study drug exposure in days})]$. A study drug interruption on a given day is defined as any interruption of the study drug on that day. A study drug interruption that continues through the end of the study participation (i.e., subject does not resume study drug before the end of the study participation) will not be included in the compliance calculation. Study drug compliance will be summarized descriptively based on the FAS by cohort and overall. It will also be summarized in categories: $<80\%$ and $\geq 80\%$, using counts and percentages.

9.2.6 Important Protocol Deviations

An important protocol deviation (IPD) is a deviation that may significantly affect the completeness, accuracy, or reliability of the study data or that may significantly affect a subject's rights, safety, or well-being. IPD rules will be developed and finalized before database lock. IPDs will be identified by the PD review team according to the protocol deviation plan.

IPDs will be summarized descriptively by cohort and overall.

9.3 Efficacy Analysis

Efficacy analyses for Treatment Period (Part A) will be based on FAS and efficacy analyses for Off-treatment Follow-up Period (Part B) will be based on Follow-up Set, unless specified

otherwise. All efficacy analyses will be conducted separately for Cohort 1 and Cohort 2, as well as combined.

9.3.1 Analysis of the Primary Efficacy Variable

9.3.1.1 Definition of the Primary Efficacy Variable

The primary efficacy endpoint is percent change from baseline in UPCR at Week 13. The Week 13 UPCR value will be calculated by averaging a maximum of 3 nonmissing UPCR values measured within a 7-day period as described in [Appendix A](#).

9.3.1.2 Analysis of the Primary Efficacy Variable

The primary efficacy endpoint will be analyzed based on combined Cohort 1 and Cohort 2. Subjects non-compliant with study drug will not be included in the analysis.

The primary analysis of the primary efficacy endpoint will be based on the following steps: (1) Log-transform the UPCR values to reduce skewness; (2) Calculate the mean of the change from baseline in log-transformed UPCR, corresponding standard error (SE) and 2-sided 80% CI; (3) The geometric mean and geometric standard error (GSE) will be calculated by back-transforming (exponential-transform) the corresponding estimates obtained in step (2). GMPC from baseline will be obtained as $[\text{geometric mean} - 1] * 100\%$. The corresponding 2-sided 80% CI will be calculated by $[\text{back-transforming (exponential-transform) the CI obtained in step (2)} - 1] * 100\%$.

The GMPC from baseline in UPCR at Week 13, GSE (%), along with the corresponding 2-sided 80% CI will be provided. In addition, the corresponding 2-sided 95% CI will be provided for descriptive purposes.

In addition, the primary efficacy endpoint will also be summarized in a similar way separately for Cohort 1 and Cohort 2.

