12.2 Analysis Sets

The following analysis sets are defined: All Subjects Set, Full Analysis Set (FAS), Safety Set, and Follow-up Set.

The **All Subjects Set** will include all subjects who were enrolled in the study. This analysis set will be used for all individual subject data listings and disposition summary tables, unless otherwise specified.

The **FAS** will include all subjects who received at least 1 dose of study drug in the Treatment Period and have at least 1 post-baseline efficacy assessment. The FAS will be used to summarize subject demographics and baseline characteristics, and for all efficacy analyses in the Treatment Period, unless otherwise specified.

The **Follow-up Set** will include all subjects who entered the Off-treatment Follow-up Period (Part B) and have at least 1 efficacy assessment in that period. The Follow-up Set will be used for all efficacy analyses in the Follow-up Period, unless otherwise specified.

The **Safety Set** will include all subjects who received at least 1 dose of study drug. The Safety Set will be used for all safety analyses, unless otherwise specified.

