12.3.3.1 Analysis of Primary Variables

The primary efficacy endpoint is percent change from baseline in UPCR at Week 13. The Week 13 UPCR value will be calculated as the average of the available UPCR measurements (maximum 3) taken during Week 13. The baseline value will be the average of the 3 UPCR values from the urine samples collected during screening.

The percent change from baseline in UPCR at Week 13 will be analyzed by first log transforming the UPCR data before analyses to reduce skewness and calculating the change from baseline in log-transformed values. The GMPC from baseline in UPCR will be estimated along with the corresponding 2-sided 80% CI. The GMPC from baseline and associated confidence limits will be calculated by back-transforming the estimated simple mean of change from baseline in log-transformed data.

Sensitivity analyses for handling missing data due to treatment or study discontinuation will be described in the SAP.

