3 MODIFICATIONS

3.1 Modifications to the Approved Clinical Study Protocol

Not applicable.

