9.3.1.3 Supportive Analyses

There will be no supportive analysis for the primary efficacy endpoint.

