9.3.1.4 Sensitivity Analysis

No sensitivity analysis for the primary efficacy variable is planned.

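### The primary UPCR analysis drops non-compliant subjects under a rule the SAP neither defines nor declares, with no full-FAS estimate beside it

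*SAP*

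**What the plan says.** Protocol Version 6.0, section 12.2, defines the FAS by at least one dose and at least one post-baseline efficacy assessment. It assigns that set to the baseline summaries "and for all efficacy analyses in the Treatment Period, unless otherwise specified". Section 12.3.3.1 adds no compliance condition for the primary endpoint and promises: "Sensitivity analyses for handling missing data due to treatment or study discontinuation will be described in the SAP". SAP 8.2 defines the FAS in the same way.

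SAP 9.3.1.2 then states: "Subjects non-compliant with study drug will not be included in the analysis". The same sentence appears four more times in 9.3.2.2: for UPCR over time, UACR at Week 13, UACR over time, and UPCR in Part B. SAP 10.1.3 carries it into any interim analysis. The by-cohort summaries in 9.3.1.2 are done in a similar way, so they are not full-FAS results either.

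On related points the SAP says:
- Section 3.1, headed "Modifications to the Approved Clinical Study Protocol", is marked not applicable.
- Section 9.3.1.3: "There will be no supportive analysis for the primary efficacy endpoint".
- Section 9.3.1.4: "No sensitivity analysis for the primary efficacy variable is planned".
- Section 9.2.5 gives a compliance percentage and tabulates it below 80% and at or above 80%, as a descriptive summary. "A study drug interruption that continues through the end of the study participation" is left out of that percentage.
- Section 9.2.6: "IPD rules will be developed and finalized before database lock".

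**The concern.** Compliance is known only after treatment starts and may be related to tolerability or to response. Removing subjects because of it selects the sample on a post-baseline event, and there is no control arm in which the same selection could be seen. The reported reduction is too large if excluded subjects respond less than the others, correct if they respond equally, and too small if they respond better. No planned estimate shows which applies, and the disposition categories in SAP 9.2.1 do not count these exclusions.

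The missing definition adds to this. The documents hold two possible measures, tablet count (protocol 10.6) and days of interruption (protocol 12.3.2.4, SAP 9.2.5), and 9.3.1.2 refers to neither. The SAP also does not say whether compliance is judged over the whole period or up to each visit. Two programmers could build different primary analysis sets. UPCR results can be seen while the study runs open-label, so a rule settled late could be settled with the results in view.

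**Working it through.** **1. The plan's own precision figure.** Inputs: SD 0.672 on the log scale, n = 10, two-sided 80% CI (protocol 12.1, SAP 7.2). Half-width = t(0.90, n-1) × SD / √n = 1.383 × 0.672 / √10 = 0.294. This matches the plan. With n = 20 (up to 10 plus about 10) the half-width is 0.1995; with n = 16 it is 0.225.

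**2. Effect of the exclusion on the estimate.** Assumptions: 20 subjects have a Week 13 value, k of them are excluded, the compliant subjects' geometric mean ratio is g = 0.5 (reported GMPC -50%), and the excluded subjects' ratio is r. Then

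all-subject ratio = exp{[(20 - k) ln g + k ln r] / 20}.

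| Excluded subjects | k = 1 | k = 4 |
|---|---|---|
| worsen by 30% (r = 1.3) | -47.6% | -39.5% |
| no change (r = 1) | -48.2% | -42.6% |
| same response (r = 0.5) | -50.0% | -50.0% |
| fall by 70% (r = 0.3) | -51.3% | -54.9% |

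For no change, k = 2 gives -46.4% and k = 3 gives -44.5%. The log-scale shift is (k/20) × ln 2, that is 0.035 for k = 1 and 0.139 for k = 4. Against the n = 20 half-width this is 0.035/0.1995 = 17% and 0.139/0.1995 = 69%. In a single cohort of 10 with no change in the excluded subjects, the all-subject figure is -46.4% for k = 1 and -42.6% for k = 2.

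**3. What happens if the 80% split in SAP 9.2.5 were the rule.** Thirteen weeks of dosing is 91 days.
- 19 interrupted days, then resumed: 100 × (1 - 19/91) = 79.1%, excluded.
- 18 interrupted days, then resumed: 100 × (1 - 18/91) = 80.2%, kept.
- Permanent stop with no earlier interruption: the final interruption is not counted and the denominator ends at the last dose, so the score is 100% and the subject is kept.

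**4. Which urine a kept stopper can contribute.** The safety follow-up visit (SFUV) falls 21 to 35 days after the last dose, and its urine is collected for efficacy use among others (protocol Table 3-3). SAP Appendix A assigns UPCR to Week 13 by study day, Days 79 to 106.
- Last dose on Day 58: SFUV on Days 79 to 93. Last dose on Day 71: SFUV on Days 92 to 106. For any last dose from Day 58 to Day 71, an SFUV held within its visit window always lands in the Week 13 window.
- Last dose on Days 44 to 85: it can land there, depending on timing.
- Last dose by Day 43: the latest SFUV is Day 78, so it cannot.

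A subject whose last dose was on Days 58 to 71 completed 58/91 = 63.7% to 71/91 = 78.0% of planned days. That subject would count as 100% compliant and could supply off-treatment urine as the Week 13 value. The subject who resumed after 19 missed days would be removed.

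**The case against.** The strongest reply has five parts.

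- **Permission.** The clause in protocol 12.2 lets the SAP vary the analysis set, and SAP section 4 says the SAP documents analyses not in the protocol. This stands: the SAP may narrow the set. It does not excuse SAP 3.1 declaring no change.
- **A natural definition exists.** The 80% split is the only compliance threshold in the SAP, so the gap may be a missing cross-reference. It is a plausible intended cut, but the text uses it only descriptively, and step 3 shows how it treats permanent stoppers. A link from the important-protocol-deviation rules to this exclusion is also only a possibility.
- **Safeguards.** The SAP must be final before an interim cut or database lock, interim work is done by a team outside study conduct, and individual listings cover all subjects. These limit hidden selection. They do not supply a rule that the final text lacks, nor a summary estimate.
- **Size.** The number excluded is assumed, and a subject who took about 79% of doses may well respond. With one exclusion and no response the change is 1.8 points. Against the n = 16 interval that would actually be reported, the largest no-change shift is 0.139/0.225 = 62% of the half-width, and it stays inside that 80% CI. All of this is fair, and it is why the range is shown in both directions.
- **Estimand.** An on-treatment estimate is defensible in a Phase 2a estimation study, and Version 2.0's summary of changes explains the one-sided Week 13 visit window as keeping primary samples on treatment. That supports a defined compliance-restricted analysis beside the full set. It does not support an undefined one standing alone. Whether off-treatment urine belongs in the primary analysis is open to argument; the SAP needs to state a rule.

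**Conclusion.** The point holds and must be fixed before any data cut. The exclusion is not in the protocol's primary analysis, is not declared in the SAP, has no operative definition, and has no full-FAS estimate beside it. The plan's stated precision is correct; the problem is who enters the estimate. With 1 to 4 of 20 subjects excluded and a reported -50%, the all-subject result could lie anywhere from -39.5% to -54.9%, depending on whether excluded subjects worsened by 30% or fell by 70%. Those counts and responses are assumptions. Off-treatment urine from retained stoppers would tend to dilute the effect if proteinuria rises again off drug, which Part B is there to explore.

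**What to change.** 1. Delete the exclusion sentence from SAP 9.3.1.2 and its four repeats in 9.3.2.2. Make all FAS subjects with a Week 13 value the primary analysis. This step suffices for the main defect.
2. If a compliance-restricted estimate is wanted, list it in 9.3.1.3 as supportive. Fix the cut in the SAP, for example the existing 80%, and use planned treatment days as the denominator so that permanent stopping counts. That denominator differs from the exposure-based one in protocol 12.3.2.4, so say so. Report the number excluded by cohort.
3. State in Appendix A how UPCR values taken after permanent discontinuation but inside the Week 13 window are handled. One option is to keep them in the primary analysis and omit them in a sensitivity analysis.
4. Put the missing-data sensitivity analysis promised in protocol 12.3.3.1 into SAP 9.3.1.4. Step 1 does not recover early stoppers, because with a last dose by Day 43 the SFUV cannot reach the Week 13 window.
5. Record any departure that is kept in SAP 3.1.

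The cost is SAP wording and one or two extra tables. The headline reduction may come out slightly less favourable.

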9.3.1.3 Supportive Analyses

There will be no supportive analysis for the primary efficacy endpoint.

9.3.1.4 Sensitivity Analysis

No sensitivity analysis for the primary efficacy variable is planned.

9.3.1.5 Subgroup Analysis

No subgroup analysis for the primary efficacy variable is planned.

9.3.2 Analysis of Exploratory Efficacy Variables

9.3.2.1 Definition of Exploratory Efficacy Variable

UPCR (and UACR) values at Week 5, Week 9 and Week 13 will be calculated as the average of the available UPCR (and UACR) measurements (maximum 3) taken during Week 5, Week 9 or Week 13 within a 7-day period as described in [Appendix A](#).

